### **8.4 Interim Analysis**

An interim analysis will occur after 10 patients (5 in each group) are recruited to determine if dosing or administration route of propranolol needs to be adjusted. This interim analysis will not include any statistical testing, but rather will be used to assess the safety of the trial.

If CREB phosphorylation will be observed in patients with epinephrine blood levels over 1nM who took propranolol, the dose of propranolol will be increased to 80mg. Exclusion criteria for this dose will be reviewed based on interim analysis.

### **Safety Review**

Safety will be addressed on a per patient basis as described in Section 5.0 and as reiterated below. Because this pilot study involves only 1 dose of medication (initially 40mg; if 40mg is not effective in inhibiting CREB phosphorylation dose will be increased to 80mg) with a peak effect expected in 1-4 hours and a half-life of 3-6 hours, the safety assessment window will be in the perioperative period for up to 4 hours after dosing. Blood pressure will be monitored at 3h and 4h after the propranolol is taken. Patients will be allowed to leave if SBP >90. If blood pressure not acceptable after 4 hours, the patient will continue to be monitored and may receive IV fluids if SBP/DBP <90/60 after 6h post dose.

If there is CTCAE grade 3 bradycardia or hypotension, then the dose for subsequent patients will be modified per section 5.2. The study will be terminated if grade 4 or 5 cardiac events attributable to propranolol dosing occur. While safety will be addressed promptly on a per patient basis, a review of all AEs will occur at the safety interim analysis after 10 patients have been accrued (5 in each group). If other safety events are identified by the investigators at this interval analysis, then the propranolol dosing may be modified for subsequent subjects as directed by Section 5.2 or in a manner designated by the PI to ensure safety of the patients.

Finally, if a safety event as described in Section 5.1.1 occurs, the study will be locked and all activities suspended for 24 hours to further evaluate patient recovery and to monitor for other potential events. If patient recovery is deemed acceptable by the PI, the trial will be unlocked with subsequent patients following the modified dose reduction plan as described in Section 5.2.

Occurrence of an SAE other than those listed above will be addressed following the SAE protocol (Appendix F).

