### **6.1 Definition of a Safety Concern**

6.1.1 Safety Concerns in this study will include bradycardia or hypotension requiring intervention by the anesthesiologist beyond standard interventions to mitigate the condition (CTCAE grade 3 or greater), or any adverse event attributable to propranolol that results in a prolonged stay in post anesthesia care unit. If any event of this nature occurs during the study, the dose will be reduced as described in Section 5.2.1 for subsequent patients.

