### **6.2 Dose Reduction**

6.2.1 If a subject has CTCAE grade 3 hypotension or bradycardia (as per section 5.1.1), the dose of propranolol will be reduced to 20 mg for subsequent patients. The study will be terminated if there is an additional CTCAE grade 3 event at the lowest dose of 20mg.

6.2.2 For any CTCAE grade 4 or 5 hypotension or bradycardia attributable to pre-operative propranolol dosing, the study will be terminated.

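### After the dose, section 8.4 checks and acts on blood pressure only, although bradycardia is a named trigger for dose reduction and stopping; biopsy patients have no scheduled post-dose heart-rate check

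*Combined protocol and SAP*

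**What the plan says.** The post-dose safety schedule is in the Safety Review part of section 8.4. It describes a single dose "with a peak effect expected in 1-4 hours and a half-life of 3-6 hours" and a safety window of up to 4 hours. Its steps are:

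- Checks: "Blood pressure will be monitored at 3h and 4h after the propranolol is taken".
- Release: "Patients will be allowed to leave if SBP >90".
- Longer stay: "If blood pressure not acceptable after 4 hours, the patient will continue to be monitored". IV fluids may follow if SBP/DBP is below 90/60 after 6 hours.

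The same section names bradycardia as a trigger: "If there is CTCAE grade 3 bradycardia or hypotension, then the dose for subsequent patients will be modified per section 5.2" (the dose-reduction rule is now section 6.2). It adds: "The study will be terminated if grade 4 or 5 cardiac events attributable to propranolol dosing occur". Section 6.2.1 opens its dose-reduction rule with "If a subject has CTCAE grade 3 hypotension or bradycardia", and 6.2.2 ends the study for either effect at grade 4 or 5 if attributable to propranolol. Section 6.1.1 lists both effects in its definition of a Safety Concern.

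Before the dose, heart rate always accompanies SBP. The exclusion criterion in 3.2 and the hold rules in 4.2 for biopsy and for prostatectomy all use SBP <120 or HR <63. In the prostatectomy pathway, an anesthesiologist also looks for hypotension and bradycardia before anesthesia. The biopsy pathway has no matching step.

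**The concern.** The protocol gives bradycardia and hypotension equal weight when it decides who may be dosed, when the dose comes down and when the study stops. Once the drug has been given, the scheduled checks look for only one of the two. A biopsy patient whose heart rate has fallen but whose SBP is above 90 meets the written condition for going home.

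What is at stake is the safety of that patient, and the information on which later dosing rests. The review after 10 patients (5 per group) may change the dose on the basis of adverse events. Without scheduled heart rates, it has no systematic bradycardia information from biopsy patients. Section 8.4 also allows an increase to 80 mg. It says the exclusion criteria will be reviewed for that dose, but not the post-dose checks, so the same blood-pressure rule would carry over.

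**Working it through.** No figure in the plan bears on this point, so the check sets the rules side by side.

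| Stage | Rule | Section | SBP/BP used | Heart rate used |
|---|---|---|---|---|
| Before dose | Exclusion | 3.2 | yes | yes |
| Before dose | Hold, biopsy | 4.2 | yes | yes |
| Before dose | Hold, prostatectomy | 4.2 | yes | yes |
| After dose | 3 h and 4 h checks | 8.4 | yes | no |
| After dose | Release | 8.4 | yes | no |
| After dose | Monitoring past 4 h | 8.4 | yes | no |

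1. **Counts.** Heart rate appears in 3 of 3 rules before the dose and in 0 of 3 steps of 8.4 after it. The IV-fluid rule is left out because it treats low blood pressure. Scheduled post-dose readings in 8.4 per propranolol patient: blood pressure 2, heart rate 0.
2. **Timing.** The stated peak-effect period is 1 to 4 h. The checks at 3 h and 4 h both lie inside it (2 of 2), so a heart-rate reading at those times would be informative.
3. **Prostatectomy.** The pre-anesthesia evaluation is a post-dose bradycardia check, because the drug is given 2 h before surgery. Counting it gives 1 of 4 post-dose steps across the protocol, but for biopsy patients the count stays at 0 of 3.
4. **Other text that might fill the gap.** Section 1.0 says that propranolol use is under continuous safety monitoring, but it names no heart-rate measurement, time or limit. Appendix G records heart rate at baseline.
5. **Patients concerned.** Thirty propranolol patients are planned (3.0). The biopsy share is not stated; 10, 20 or 30 is assumed for illustration.
6. **Readings needed.** Added values = 2 × n. All planned propranolol patients: 2 × 30 = 60. Biopsy patients only: 2 × 10 = 20, 2 × 20 = 40 or 2 × 30 = 60. If recruitment is topped up under 3.0 to, say, 35 propranolol patients (an assumption): 2 × 35 = 70.

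**The case against.** The strongest reply is that the trigger is not a heart-rate value. Section 6.1.1 defines the Safety Concern by what the anesthesiologist has to do, or by a longer post-anesthesia stay. Section 6.0 refers to the propranolol/surgery group. The rule thus appears to be built around anesthesia care, where a bradycardia evaluation is required. On that reading, a missing heart rate in the release sentence changes no stopping or dose decision. This stands in part: no heart-rate value is a trigger, and no missed grade 3 event is shown. But 6.2.1 speaks of any subject, Group 1 in Appendix B includes biopsy patients, and 8.4 repeats the bradycardia trigger without limiting it to surgery.

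There are also mitigations. Men with HR <63 are excluded or not dosed, only one dose is given, adverse events are handled patient by patient and reviewed after 10 patients, and the release wording is permissive, so staff may keep a patient. These lower the likely consequence, but none of them schedules a heart-rate reading after the dose.

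Two further cautions are fair. The counts above are counts of rules and do not measure risk. The Surgery Day Worksheet (Appendix N) is weak evidence: its readable part has no field for the required blood pressures either, so its silence on heart rate is not relied on here.

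Finally, it can be said that the fix should cover biopsy patients only. The existing 8.4 checks do not distinguish the two pathways, and one rule for all costs at most 60 values in the planned sample.

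**Conclusion.** The concern holds. As written, the post-dose checks, the release condition and the decision to keep monitoring in 8.4 rest on blood pressure alone. The readable text schedules no post-dose heart rate for biopsy patients, although bradycardia is one of two named cardiac effects that change the dose or stop the study. The gap is 0 heart-rate readings against 2 blood-pressure readings per patient, and it concerns the biopsy share of 30 planned propranolol patients.

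The conclusion rests on the readable text; the schema and some form tables could not be seen, and routine care may include a pulse. It has no effect on the primary analysis. The change should be made because it is cheap and closes a gap in a written safety rule.

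**What to change.** In section 8.4:

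1. Record heart rate together with blood pressure at 3 h and 4 h for every propranolol patient.
2. Allow release only if SBP is >90 **and** heart rate is above a threshold set by the sponsor's clinicians.
3. Continue monitoring after 4 h if either condition is not met.

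The other safety and reporting rules stay as they are. The cost is two recorded values per propranolol patient: 60 for the 30 planned, and 2 for each one added by a top-up. A patient with a low heart rate may occasionally stay longer. No extra visit or procedure is needed.

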Beta blockers are commonly administered in the perioperative period. Perioperative beta blocker use has been associated with lower 30-day mortality rates, although the benefit is stronger for those undergoing cardiovascular surgery, and the benefit in the setting of non-cardiac surgery remains controversial . In a 1991 study of women in the perioperative period, a one-time preoperative dose of oral propranolol of 80 mg was well-tolerated and resulted in less anesthetic use . In a more recent randomized study, perioperative doses of 20mg or 40mg were used to reduce anxiety among surgery patients. With the administration of 20mg of oral propranolol, there was a significant decrease in anxiety with fewer cardiovascular effects than the 40mg dose. In the current study, the use of propranolol will be continuously monitored for safety events. Any safety concerns that arise as defined in the protocol will trigger a dose reduction for subsequent patients. Additionally, an interim analysis will assess safety.

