#### **4.2 Methods**

#### **Compare activation of ADRB2/PKA/BAD signaling pathway in the prostate glands of men who take or do not take ADRB2-selective beta blockers**

##### **Patients scheduled for prostate biopsy.**

The research staff screens the OR and clinic schedules for potential patients and provides a list to the investigator. [name] or co-Investigator will discuss the study with the patient and inform the research nurse or coordinator (research staff) about the patients who agreed to participate in the study. Research staff will inform Tissue Procurement Lab (Director [name]; [name], Tumor Procurement Coordinator) and courier about the scheduled date and time when prostate samples will be collected.

On the day of sample collection [name] lab will prepare box with dry ice for prostate biopsy samples, a box with wet ice for blood samples as well as 2 ml cryovials (Corning, cat#430488) to collect biopsies and tubes to collect blood (Na heparin, green-capped tube, 10 ml total blood volume).

Courier will pick up boxes from Tissue Procurement Lab (Director [name]; [name], [contact]) and deliver to research staff at Charlois clinic ([name]).

Recruited patients scheduled for prostate biopsy will be randomized into two groups. Group one will receive 40 mg propranolol given by research nurse 2 hours prior to prostate biopsy. The research nurse should withhold drug and contact treating physician if SBP <120 or HR < 63. Group two will receive no treatment.

All patients will fill out stress surveys on the biopsy day.

All patients will give approximately 10 mL of blood approximately 20 min prior to prostate biopsy to test plasma catecholamine levels (collected in 10 mL green top tube (sodium heparin) and sent on ice within 1 hour to clinical lab for processing) and propranolol level (collected in 10 mL green top tube (sodium heparin) and sent on ice to The Tissue Procurement lab for processing and storage as described below). For group one that takes propranolol, this blood sample will be drawn at 1.5 -2 hours after taking the propranolol tablet.

For the biopsy, at least 1 core of the prostate specimen is to be flash frozen (on dry ice -80C) for laboratory analysis. Each biopsy sample will be collected into separate cryovials. The samples will be picked up by courier at Charlois clinic and delivered to Tissue Procurement laboratory.. The tissue samples will be frozen at -80 C.

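### The only scheduled review of all adverse events comes when at most about five men have had 40 mg; none is scheduled at 80 mg, although the same interim can raise the dose

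*Combined protocol and SAP*

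**What the plan says.** Section 8.4 sets one interim: "An interim analysis will occur after 10 patients (5 in each group) are recruited". Its stated purpose is "to determine if dosing or administration route of propranolol needs to be adjusted". It involves no hypothesis test: "This interim analysis will not include any statistical testing, but rather will be used to assess the safety of the trial". The Safety Review text places the aggregate look at adverse events at the same point: "a review of all AEs will occur at the safety interim analysis after 10 patients have been accrued (5 in each group").

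The next paragraph of 8.4 attaches an activity rule to the same look. If CREB phosphorylation is seen in treated men whose epinephrine exceeds 1 nM, "the dose of propranolol will be increased to 80mg". The only review that 8.4 ties to 80 mg is of the exclusion criteria for that dose, and it is to be based on the interim. The Safety Review text repeats the possible move from 40 mg to 80 mg without a time point.

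The Safety Review also says that investigators may modify dosing for safety events other than the defined ones, if they identify them at this look. Neither 8.4 nor Section 11.0 schedules a later aggregate review. Section 11.0 gives the principal investigator overall responsibility for monitoring, without a timetable.

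On counting patients, 8.4 says recruited and the Safety Review says accrued. Section 4.2 allows an allocated man to go undosed on the day. For biopsy patients: "The research nurse should withhold drug and contact treating physician if SBP <120 or HR < 63". The prostatectomy text uses the same thresholds.

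**The concern.** The interim serves two purposes that pull apart. It is the one occasion on which all adverse events are read together, and it is also where the dose may double. If the dose does rise, the review will have covered a dose no longer in use, and the dose then given to most of the propranolol group will have no equivalent review.

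What could be missed is a pattern rather than a single severe event: several men with grade 1 or 2 hypotension, light-headedness or similar effects, none of which alone meets a rule. The plan's own background treats dose as relevant to tolerability. Of 20 mg it reports that "there was a significant decrease in anxiety with fewer cardiovascular effects than the 40mg dose".

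The recruitment trigger adds a smaller problem. Under Sections 4.1 and 4.2, registration follows within 24 hours of consent, includes group assignment, and can precede the procedure. Ten recruited patients may therefore mean fewer than five men dosed when the review takes place.

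**Working it through.** The plan states no detection probability or other operating figure for the safety review, so there is none to reproduce. The stated 80% power for the primary comparison does reproduce (79.9% by the noncentral t with 25 per group, difference 0.21, SD 0.26), but nothing here depends on it.

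**Step 1. What applies at each dose.**

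| Safeguard | Where | At 40 mg, up to interim | At 80 mg, after interim |
|---|---|---|---|
| Aggregate review of all AEs | 8.4, Safety Review | Yes, once | None scheduled |
| Power to act on events outside the defined rules | Safety Review | Yes, at that look | Not provided for |
| Review of exclusion criteria for 80 mg | 8.4 | – | Yes, but from 40 mg data |
| Grade 3, 4 and 5 rules for hypotension and bradycardia | 6.1, 6.2 | Yes | Yes |
| Propranolol-attributable AE that prolongs the post-anesthesia stay | 6.1.1 | Yes | Yes |
| 24-hour study lock after a defined event | Safety Review | Yes | Yes |
| Blood pressure at 3 h and 4 h | Safety Review | Yes | Yes |
| DSMC reporting (unexpected grade 4, grade 5, unplanned hospitalization over 24 hours at any grade) | 13.3, Appendix F | Yes | Yes |

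Only the first two rows look across patients at lower-grade events, and neither recurs.

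**Step 2. How many men.** Section 3.0 plans 30 men on propranolol. At most 5 are dosed by the interim, so 30 − 5 = 25 remain, and 25/30 = 83%. This is a ceiling for the planned arm, because it needs the dose to switch at once. The trigger needs western blot results, and accrual is 5 per month (Section 8.5), or about 2.5 propranolol men per month. If recruitment continues, each month's delay lowers the figure by about 2.5: 22.5 men after one month, 20 after two.

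**Step 3. What five men can show.** The documents give no event rates, so the rates p below are assumptions. The chance of at least one event among n men is 1 − (1 − p)^n.

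| Assumed p | n = 5 | n = 25 | Expected events in 25 |
|---|---|---|---|
| 5% | 1 − 0.95^5 = 22.6% | 72.3% | 1.25 |
| 10% | 1 − 0.90^5 = 41.0% | 92.8% | 2.5 |
| 20% | 1 − 0.80^5 = 67.2% | 99.6% | 5 |

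If none of the five men at 40 mg has an event, the exact one-sided 95% upper bound on the true rate at that dose is 1 − 0.05^(1/5) = 45.1%. That bound says nothing about 80 mg, for which the review has no data.

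**The case against.** The best case against the point is that this is a single-dose pilot with a dense set of event-driven rules, and that a second tabulation is a reviewer's preference. Much of this stands. A reader might infer that men at 80 mg would be unmonitored, or covered only by rules for grade 3 and above. The documents do not support that. Section 6.1.1 has no grade threshold for a propranolol-attributable event that prolongs the post-anesthesia stay. Appendix F requires all AEs to be entered in WISER and sends longer unplanned hospitalizations to the DSMC whatever their grade. Section 1.0 promises continuous monitoring.

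Nor do the documents show 80 mg to be unsafe. Section 1.0 also reports that one preoperative 80 mg dose was well tolerated in a 1991 study of women. And the statement in Section 1.0 that an interim will assess safety is not made untrue by a dose increase, since it promises nothing for each dose.

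Two further objections are fair. Five men is a weak look: it misses an event of 20% frequency 33% of the time and one of 10% frequency 59% of the time. And because Section 3.2 excludes men at the same blood pressure and heart rate thresholds as the day-of-procedure check, withheld doses may be few.

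What remains is narrower. Continuous entry of single events is not a scheduled reading of them together. The plan judged such a reading worth doing at 40 mg with about five dosed men, and gives no reason to omit it at a higher dose.

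**Conclusion.** The gap is real but limited. One aggregate AE review is scheduled, at 40 mg, and none at 80 mg if the same interim raises the dose. The authority to act on events outside the defined rules is tied to that one look. At most 25 of 30 propranolol men (83%) would be affected. That figure assumes the dose does rise, that it switches immediately, and that the arm stays at 30. The control group is not affected. The detection probabilities of 41% and 67% rest on assumed rates of 10% and 20%. Counting men recruited rather than dosed is a secondary weakness whose size the documents do not allow to be estimated.

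A reader might go further and conclude that dosing has to stop until a review at the new dose is complete. That is a clinical rule for the sponsor, and this point does not call for it. It is a worthwhile, inexpensive improvement to safety oversight, not a flaw in the primary analysis.

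**What to change.** In Section 8.4, make two wording changes:

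1. State that the same non-statistical review of all AEs is repeated once five men have actually received any new dose reached under 8.4, with the same authority to act on other events.
2. Trigger the first review by five men dosed with propranolol, instead of 10 patients recruited.

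Leave the dose rules unchanged, and leave to the sponsor whether dosing pauses during a review.

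The sponsor should also reconcile these passages with the possible increase to 80 mg:

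- Section 8.4 describes the interim as a safety assessment, yet a CREB finding at that look raises the dose.
- Section 6.2.1 on dose reduction does not mention 80 mg.
- Section 14.2 says that 40 mg tablets will be used.
- The Safety Review cites Sections 5.1.1 and 5.2 for rules that now stand in 6.1 and 6.2.

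The cost is a few sentences of protocol text and, only if the dose changes, one extra short AE listing for the investigators to read. The first review may fall slightly later than under the recruitment trigger.

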### **8.5 Accrual Rate**

The accrual rate is anticipated to be 5 per month, thus recruitment should be complete within 12 months. Since analysis will occur on the samples that are taken during prostate biopsy, the overall length of this study is anticipated to be less than 18 months (allowing for the possibility that accrual goes slower than predicted or that time for lab analyses takes some time to be performed).

## **9.0 Data Management**

Informed consent document	
Subject Eligibility Checklist (Appendix A)	
Protocol registration form (Appendix B)	WISER
Perceived Stress Form (Appendix C)	REDCap
Distress Thermometer (Appendix D)	REDCap
Adverse Events Log (Appendix E)	WISER

Baseline Medical History Form (Appendix G)	WISER
Tissue Collection Form (Appendix H)	
Blood Collection Form (Appendix I)	
Data Collection Form (prostate pCREB and pBAD) (Appendix J and K)	REDCap
Plasma Outcomes Form (Appendix L)	REDCap
RNA Data Collection Form (Appendix M)	REDCap
Surgery Day Worksheet (Appendix N)	

